Enrollment has begun for the BEST3 trial in the United Kingdom. The BEST3 Trial will assess whether the Cytosponge test for patients with reflux symptoms will be effective in increasing the detection of Barrett's esophagus in primary care and to evaluate its cost effectiveness. It will also give further information on the diagnostic accuracy of the Cytosponge test and will also evaluate the patient acceptability of this new diagnostic test. This is a study of over 9,000 patients and is being conducted in primary care clinics throughout the UK. Eligible subjects are invited for Cytosponge testing, with follow up endoscopy performed for those with a positive test. Additionally, a subset of patients ineligible for testing or who test negative will be invited to undergo upper endoscopy.

We now propose to study the Cytosponge test in the primary care setting here in the United States to assess participation rates, tolerability, safety, and performance. In addition to testing samples for TFF3, we will also assess for p53 expression; emerging data indicates that p53 expression is an important predictor of future dysplastic Barrett's esophagus or esophageal adenocarcinoma.

2. Objectives

Primary Objective

The primary objective of the study is to pilot a Barrett's esophagus screening program using the Cytosponge test in the primary care setting. This will be assessed by two outcomes: 1) participation rates among eligible patients seen at CUMC primary care practices; and 2) patient tolerability of the Cytosponge test as assessed by questionnaire.

Secondary Objectives

Secondary objectives include the following:

- To assess the positive predictive value of the Cytosponge test in the primary care setting. We will calculate the proportion of patients with a positive Cytosponge test who have Barrett's esophagus confirmed on follow up endoscopy.

- To assess safety of the Cytosponge test in the primary care setting.

3. Overview of Study Design

We will prospectively enroll 100 patients to undergo Cytosponge testing. We plan to use data generated from this study to design a follow up study, refining patient selection and recruitment methods as necessary.

Study Population

General Considerations

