The purpose of Cytosponge testing is to identify patients with Barrett's esophagus, so that surveillance can be instituted to facilitate the early detection of dysplasia and cancer, and interventions can be instituted to reduce esophageal cancer mortality. The risk of BE varies greatly by age, sex, race, and other factors including a history of GERD symptoms, obesity, and smoking. Inclusion and exclusion criteria have been developed in order to maximize BE detection, but without being too restrictive in patient selection. While difficult to anticipate precisely, we have designed criteria for screening with the goal of diagnosing BE in 5-10% of screened patients.

Inclusion Criteria

Males:

- Ages 50-75 AND at least one of the following:
 - Gastro-esophageal reflux disease (GERD)*
OR
 - Family history (first degree relative) with Barrett's esophagus or esophageal adenocarcinoma
OR
 - $BMI \geq 30$
OR
 - History of cigarette smoking (at least 10 pack years)

Females:

- Ages 50-75 AND GERD* AND either:
 - Family history (first degree relative) with Barrett's esophagus or esophageal adenocarcinoma
OR
 - $BMI \geq 30$
OR
 - A history of cigarette smoking (at least 10 pack years)

*GERD defined as either a history of frequent heartburn or fluid regurgitation symptoms (at least weekly for 6 months) OR regular use of proton pump inhibitors or histamine-2 receptor antagonists.

Exclusion Criteria

- History of gastric or esophageal cancer
- History of esophageal surgery
- Known untreated esophageal stricture or uninvestigated dysphagia
- Previous upper endoscopy within 10 years
- Cancer within 3 years except for non-melanoma skin cancer

- Portal hypertension, with or without known varices
- Uncontrolled coagulopathy
- Uncontrolled major comorbid illness
- Inability to tolerate or contraindication to upper endoscopy
- Inability to give informed consent

Identification of Study Subjects

The schedules will be reviewed from participating primary care providers (PCPs). The electronic medical records will be reviewed to identify potentially eligible study subjects. Additionally, the study team will work with CUIMC IT department and TRAC committee to generate a recurring report using the inclusion/exclusion criteria of the study. The TRAC report will list patients with upcoming appointments with participating PCPs who are potentially eligible study subjects, based on the information already present in their electronic medical records.

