The insurance of potentially eligible subjects will be ascertained to determine whether a possible follow up endoscopy would be in-network or out-of-network. The participating PCPs will be notified of which subjects are potentially eligible. During the subject's office visit, the PCP will introduce the study to the patient prior to a member of the research team contacting the patient. If the patient indicates to the PCP that they are not interested in participating in the research study, the research team will not approach the patient.

Informed Consent

At the conclusion of the visit with the PCP, a member of the Research Team will approach the subject regarding participation in the study, including background of the proposed study, inclusion and exclusion, the benefits and risks of participation. If this is of interest to the subject, the informed consent form is discussed and presented. The subject must sign the consent form prior to enrollment.

Study Procedures

The Cytosponge (Medtronic) is a tethered capsule on a string that a patient can swallow while sitting in a chair in an office. The capsule dissolves, exposing a small spherical brush. After 5 minutes, the string with the attached sponge is then withdrawn from the patient, capturing a small sample of cells from the esophagus that can accurately determine whether or not a patient has Barrett's esophagus.

The Research Nurse will conduct all procedures by asking subjects to be seated upright and swallow the tethered capsule sponge with sips of water. After an interval of 5 min, the capsule sponge will be pulled out with steady traction using the string attached to the capsule sponge. The sponge will then be placed in 20 mL CytoRich Red Preservative Fluid. Subjects will then complete a tolerability questionnaire which allows patients to grade discomfort during the procedure on a Likert scale of 0-10. Participants will also be asked if they would have the procedure again (yes/no).

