Immunohistochemical testing for trefoil factor 3 (TFF3) and p53 expression is performed on tissue samples collected from the Cytosponge. The subject exits the study in the event of a negative TFF3 test and normal p53 expression. In the event of a positive TFF3 test or abnormal expression of p53, the subject will be informed of the test results and scheduled for an upper endoscopy. During the upper endoscopy, notation will be made with regard to endoscopic evidence of Barrett's esophagus and any other endoscopic findings. If Barrett's esophagus is suspected, four-quadrant biopsies will be taken every 2 cm per standard clinical practice to assess for the presence of intestinal metaplasia and/or dysplasia.

Study Evaluations

The primary outcomes will be:

- Participation rates – defined as the proportion of patients who agree to undergo Cytosponge testing among number of eligible patients offered Cytosponge testing.
- Tolerability – after undergoing the Cytosponge test, subjects will be asked to rate tolerability using a Likert scale (1 to 10) and whether they would be willing to undergo Cytosponge testing again.

Secondary outcomes of Cytosponge testing include:

- Positive predictive value of the Cytosponge TFF3 test: $PPV = (\# \text{ of patients with endoscopic and histologic evidence of Barrett's esophagus on upper endoscopy}) / (\# \text{ of patients with TFF3-positive Cytosponge test who undergo a follow up endoscopy})$
- Positive predictive value of the Cytosponge p53 expression test: $PPV = (\# \text{ of patients with endoscopic and histologic evidence of Barrett's esophagus associated dysplasia on upper endoscopy}) / (\# \text{ of patients with abnormal p53 Cytosponge test who undergo a follow up endoscopy})$
- Safety: we will record and report all adverse events (AEs) and serious adverse events (SAEs) related to Cytosponge testing.

Statistical Methods

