Data will be summarized with proportions, means, or medians as appropriate with 95% confidence intervals. The sample size of 100 patients was chosen as a convenience sample that represents a feasible enrollment target and that will provide critical data for the design of larger Cytosponge testing studies. We have developed the inclusion and exclusion criteria such that the anticipated prevalence of BE in the study population will range from 5-10%. With a 5% true BE prevalence in our study population, 11% of subjects are expected to test TFF3-positive. With a 10% true BE prevalence, 15% of subjects are expected to test TFF3-positive

4. Risks and Benefits Assessment

Risks

Cytosponge testing is overall well tolerated. In the aforementioned BEST2 trial [11], 97.9% of patients rated the experience (undergoing Cytosponge testing) as 3/10 (mildly unpleasant) or higher. There were three serious adverse events, none of which were attributed to the Cytosponge. On endoscopy, 16.7% of patients had mild oozing of blood in the esophagus from the Cytosponge, but there were no cases of major bleeding.

In total, over 9,000 patients have undergone testing with the Cytosponge (EuroPlaz, United Kingdom) in the United Kingdom and the United States. Three detachments have occurred (<1 in 1,000) upon withdrawal of the tethered device. In all cases, the Cytosponge was retrieved by endoscopy, and subjects recovered without further complications.

Cytosponge testing may produce false positive results, which may lead to undue anxiety and worry. Additionally, patients with a positive Cytosponge test but without Barrett's esophagus will still undergo a follow up endoscopy. Severe complications from upper endoscopy are rare (<1%), and include bleeding infections, aspiration, and intestinal perforation.

Benefits

There are no direct benefits to participation in the study. Detection of Barrett's esophagus by undergoing Cytosponge testing could lead to early detection of dysplasia or esophageal adenocarcinoma. However, it is unclear whether early detection leads to lower esophageal cancer mortality or improved outcomes overall.

Adverse Event Reporting

Adverse Event Classification Definitions

All adverse events (AEs) will be recorded. The intensity of adverse events will be evaluated using the following criteria:

- Mild – noticeable to the patient but does not interfere with routine activity

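### The exclusions do not name prior Barrett's esophagus, so a diagnosis more than 10 years old with no endoscopy since stays eligible and can count in both secondary PPVs

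*Combined protocol and SAP*

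**What the plan says.** The Exclusion Criteria in section 3 of the protocol have ten items. Those closest to this point concern gastric or esophageal cancer, esophageal surgery, stricture or dysphagia, and "Previous upper endoscopy within 10 years". None names BE, and no inclusion criterion requires the patient to be free of a BE diagnosis.

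Candidates are found by chart review and by a recurring report (the TRAC report) that applies the written criteria, "based on the information already present in their electronic medical records" (Identification of Study Subjects). The research team's discussion with the patient then covers the study, "including background of the proposed study, inclusion and exclusion, the benefits and risks of participation" (Informed Consent, section 3).

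The secondary objective counts patients with a positive test "who have Barrett's esophagus confirmed on follow up endoscopy". Under Study Evaluations the TFF3 PPV has as its denominator the number "of patients with TFF3-positive Cytosponge test who undergo a follow up endoscopy". The p53 PPV has the same form, with BE-associated dysplasia as the finding. Neither is limited to new diagnoses.

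On purpose, General Considerations states: "we have designed criteria for screening with the goal of diagnosing BE in 5-10% of screened patients". The Overview of Study Design adds: "We plan to use data generated from this study to design a follow up study".

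**The concern.** A screening PPV is normally read as the chance that a positive test uncovers disease not known before. Here the eligibility list leaves one narrow route by which an already diagnosed patient can enter, and the PPV definitions count that patient like any other. Finding known BE again adds a true positive that a screening program in undiagnosed people would not have produced, so the PPV would be higher than in a population with no prior diagnosis. Because the results are meant to inform a follow-up study, a PPV that may mix new and known BE is harder to carry forward. A confidence interval does not reveal this, since it is a question of who is counted and not of sampling error.

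**Working it through.** **Step 1: who remains eligible.** Section 1 states that BE can be diagnosed only by upper endoscopy. A known diagnosis therefore implies an earlier endoscopy, and the 10-year rule removes everyone diagnosed or re-examined in that period. What remains is a patient whose diagnosis is more than 10 years old, who has had no endoscopy since, and who meets all other criteria. Chart review, the TRAC report and the consent discussion all work from the written list, so no written step asks about such a diagnosis.

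**Step 2: how that patient reaches a PPV.**
- TFF3: the BE persists, TFF3 is positive and the follow-up endoscopy is done. The patient is then in numerator and denominator.
- p53: p53 is abnormal and the endoscopy is done. The patient enters the denominator, and also the numerator if dysplasia is found. The documents give no accuracy figures for p53, so no size is computed for it.

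**Step 3: reproduce the plan's own figures.** Inputs are sensitivity 79.9% and specificity 92.4% (section 1), so the false-positive rate is 0.076; n = 100; and prevalence p = 5% or 10% (Statistical Methods).
- p = 5%: true positives 5 × 0.799 = 3.995; false positives 95 × 0.076 = 7.220; total 11.215. This matches "With a 5% true BE prevalence in our study population, 11% of subjects are expected to test TFF3-positive". Implied PPV is 3.995/11.215 = 35.6%.
- p = 10%: 10 × 0.799 = 7.990; 90 × 0.076 = 6.840; total 14.830, matching the stated 15%. Implied PPV is 7.990/14.830 = 53.9%.

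**Step 4: effect of k previously diagnosed patients per 100.** The documents do not give k. I assume 0.1, 0.5 and 1, and that attendance at endoscopy does not depend on prior diagnosis.
- Baseline A, persisting cases come on top of the stated prevalence: TP = (100 − k) × p × 0.799 + k × 0.799; FP = (100 − k) × (1 − p) × 0.076. The PPV is compared with the step 3 value.
- Baseline B, the stated prevalence already includes them: the PPV as defined stays at the step 3 value. Without them, TP = (100p − k) × 0.799 and FP = 100 × (1 − p) × 0.076.

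| p | k | A: PPV with them | A: change | B: PPV without them | B: change |
|---|---|---|---|---|---|
| 5% | 0.1 | 4.071/11.284 = 36.1% | +0.5 | 3.915/11.135 = 35.2% | −0.5 |
| 5% | 0.5 | 4.374/11.558 = 37.8% | +2.2 | 3.596/10.816 = 33.2% | −2.4 |
| 5% | 1 | 4.754/11.902 = 39.9% | +4.3 | 3.196/10.416 = 30.7% | −4.9 |
| 10% | 0.1 | 8.062/14.895 = 54.1% | +0.25 | 7.910/14.750 = 53.6% | −0.25 |
| 10% | 0.5 | 8.350/15.155 = 55.1% | +1.2 | 7.591/14.431 = 52.6% | −1.3 |
| 10% | 1 | 8.709/15.481 = 56.3% | +2.4 | 7.191/14.031 = 51.3% | −2.6 |

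Changes are in percentage points, taken before rounding.

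If the old BE is no longer present, the patient can only add to the false positives. For k = 1 on baseline A, the PPV is 3.955/11.179 = 35.4% and 7.910/14.758 = 53.6%, slightly below step 3.

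**Step 5: compare with the precision available.** Exact (Clopper-Pearson) 95% intervals at about the expected counts are 10.9–69.2% for 4/11 and 26.6–78.7% for 8/15. Removing one true positive gives 6.7–65.2% for 3/10 and 23.0–77.0% for 7/14.

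**The case against.** The 10-year rule already does most of the work. The remaining patient must have an old diagnosis, no endoscopy since, age 50–75 with the required risk factors, persisting BE, a positive test and a completed endoscopy. There may be none. That stands, and it is why the point is small.

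The comparison with an undiagnosed population is also not in the PPV definitions. Under those definitions persisting BE is a true positive, and General Considerations gives the purpose as identifying BE so that surveillance can begin, with criteria that are not too restrictive. A patient lost to endoscopy for over 10 years arguably fits that purpose. This weakens the point but does not remove it: the documents speak of a screening program and of diagnosing BE, which points to undiagnosed patients, and no operative criterion says so.

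The assumed frequencies may be generous. At 5% prevalence, k = 0.1, 0.5 and 1 mean that 2%, 10% and 20% of all BE in the sample was diagnosed long ago and not re-examined. The only related figure is in section 1: more than 90% of esophageal adenocarcinoma patients had no earlier BE diagnosis. That is a different population and does not fix k, but the largest value should not be read as the expected one.

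A reader might infer that the PPVs are miscalculated, that known BE is broadly admitted, or that the participation, tolerability or expected-positive figures are compromised. The documents support none of these. The PPVs follow their definitions, and the 10-year rule leaves one route only. The primary outcomes do not depend on BE status as defined, and the 11% and 15% are conditional on the stated prevalence and reproduce. Nor should the effect be read as confined to TFF3, because the p53 PPV is open to the same patients.

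**Conclusion.** The gap is real but narrow. The written criteria admit a patient with a BE diagnosis more than 10 years old and no endoscopy since, and both secondary PPVs can count that patient. The size is conditional on an unknown number: for 0.1 to 1 persisting case per 100, the TFF3 PPV differs by about 0.5 to 4.9 points at 5% prevalence and about 0.25 to 2.6 points at 10%. With no such patients there is no effect. These figures assume that the sensitivity and specificity quoted in section 1 apply to this population and to previously diagnosed patients, and that follow-up endoscopy is equally likely with or without a prior diagnosis. All are small beside intervals more than 50 points wide. This is an inexpensive improvement to consider, affecting how two descriptive secondary outcomes are read; it is not a flaw in the study's primary results.

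**What to change.** Add one exclusion: *Known or previously diagnosed Barrett's esophagus (any date)*. Apply it in the chart review and the TRAC report, and ask the patient directly at the eligibility discussion, because a diagnosis of that age may not be in the electronic record.

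For patients already enrolled, establish prior BE status from the chart and, at least for those with a positive TFF3 or abnormal p53 test, by asking the patient. A chart check alone would miss unrecorded diagnoses, so a count of zero based on it would not be reliable. Report the number with a prior diagnosis even if it is zero. If it is not zero, give the TFF3 and p53 PPVs both as defined and without those patients.

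The cost is one line in the criteria, one filter in an existing report, one question to the patient, and a short status check of at most 100 patients, with the question needed for roughly the 11–15 expected to be TFF3-positive plus any others with abnormal p53. The downside is a very small loss of otherwise eligible patients.

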**Protocol Title: The Acceptability of a Rapid Esophageal
Adenocarcinoma Risk Test (REACT)**

NCT03366012

STUDY PROTOCOL

Date: November 30, 2022

Principal Investigator:

[name], MS

Co-Investigators:

[name]

1. Background and Rationale for Study

The incidence of esophageal adenocarcinoma (EAC) has risen 10-fold over the past half century and continues to have a dismal prognosis. [1-3] Even though it has been established that Barrett's esophagus (BE) is the precursor lesion to EAC, more than 90% of EAC patients are never diagnosed with BE beforehand. [4-6] Thus, the opportunity is missed to identify most patients at high risk for EAC who could benefit from surveillance and early endoscopic therapy, which in turn may lower EAC mortality. [5, 7-9] Upper endoscopy is the only means to diagnose BE, yet widespread endoscopic screening is impractical and expensive. There is an urgent need to develop minimally-invasive methods of BE screening that can be easily performed in the primary care setting to allow for efficient and cost-effective interventions to decrease EAC mortality.

The Cytosponge is a tethered cell sampling device that is swallowed and then withdrawn through the mouth. Prior studies have shown that, using this device, immunohistochemical staining for trefoil factor 3 (TFF3) is specific for Barrett's esophagus tissue. [10] In a large case-control study (BEST2 [11]) of 647 patients with BE and 467 patients without BE, the Cytosponge was administered prior to upper endoscopy. The test was associated with 79.9% sensitivity and 92.4% specificity. The large majority (93.9%) of patients were able to swallow the Cytosponge successfully, and 97.9% of patients rated the experience as 3/10 (mildly unpleasant) or higher. There were three serious adverse events, none of which were attributed to the Cytosponge. On endoscopy, 16.7% of patients had mild oozing of blood in the esophagus from the Cytosponge, but there were no cases of major bleeding.

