- Procedure-Related: An adverse event is considered to be procedure-related when it is reasonable to believe that the event is not specific to the investigational device. Other products may have contributed to the occurrence of the event.
- Pre-Existing Condition Related: An adverse event is considered to be related to a pre-existing condition when it is reasonable to believe that the event is associated with the subject's pre-existing condition and is not specific to the investigational device or procedure. Pre-existing conditions that are exacerbated after the index procedure and have been determined to not be device- or procedure-related will be categorized as related to a pre-existing condition.
- Concomitant Medications: An adverse event that is associated with concomitant medications and is not otherwise specific to the investigational device.
- Intercurrent Condition: An adverse event that is believed to be directly associated with a new medical condition/co-morbidity/diagnosis that arises following the index procedure.
- Intercurrent Intervention: An adverse event that arises from, or is associated with, an intervention that was performed after the index procedure for reasons other than to address a device- or procedure-related complication.

Data and Safety Monitoring Plan

The PI and study team will continuously monitor any and all AE's and UP's as they arise.

The Herbert Irving Comprehensive Cancer Center (HICCC) DSMP board, led by [name], will conduct the data and safety monitoring, together with an independent internal study monitor. The initial review will consist of a comprehensive evaluation of the first 3 patients enrolled, and then will commence annually. Safety, regulation accountability, and enrollment data will be reviewed by the study monitor. Any unanticipated problems and unanticipated adverse device effects will be reported promptly to the Columbia University IRB, no later than 7 days after the occurrence or PI knowledge of the event.

5. Costs

There will be no costs to the subject for Cytosponge testing. Follow up upper endoscopy will be performed in patients with a TFF3-positive test or abnormal p53 expression to confirm a Barrett's esophagus diagnosis. The endoscopy will be billed to the patient's insurance as standard of care.

6. Subject Completion

Completion

Subjects complete participation in the study upon receiving a negative Cytosponge test or after the follow up endoscopy in the event of a positive Cytosponge test.

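### Neither PPV numerator is restricted to the marker in its denominator, so disease found in a patient positive only on the other marker inflates the PPV

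*Combined protocol and SAP*

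**What the plan says.** Section 3, Study Evaluations, gives two explicit PPV formulas as secondary outcomes.

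- **TFF3:** the numerator is the number of "patients with endoscopic and histologic evidence of Barrett's esophagus on upper endoscopy"; the denominator is the number of "patients with TFF3-positive Cytosponge test who undergo a follow up endoscopy".
- **p53:** the numerator is the number of "patients with endoscopic and histologic evidence of Barrett's esophagus associated dysplasia on upper endoscopy"; the denominator is the number of "patients with abnormal p53 Cytosponge test who undergo a follow up endoscopy".

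Entry to endoscopy is by either marker. Study Procedures schedules it "In the event of a positive TFF3 test or abnormal expression of p53", and section 5 (Costs) repeats the rule: "Follow up upper endoscopy will be performed in patients with a TFF3-positive test or abnormal p53 expression". Only patients negative on both markers leave without endoscopy.

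Section 2, Secondary Objectives, describes a single PPV: the share of patients with a positive Cytosponge test whose BE is confirmed at endoscopy. It does not say which marker makes the test positive, and it does not mention dysplasia. On analysis, Statistical Methods says only: "Data will be summarized with proportions, means, or medians as appropriate with 95% confidence intervals".

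**The concern.** A PPV is a proportion: everyone in the numerator must also be in the denominator. If TFF3 alone led to endoscopy, the missing condition would do no harm. Because either marker is enough, the endoscopy group includes by design patients positive on one marker only. Two kinds of patient then break the formulas:

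- A TFF3-negative, p53-abnormal patient with BE enters the TFF3 numerator but not its denominator.
- A TFF3-positive, p53-normal patient with BE-associated dysplasia enters the p53 numerator but not its denominator.

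Each such patient can only raise the ratio. The result is then not a binomial proportion, it is not bounded by 1, and a binomial version of the planned 95% confidence interval does not apply. PPV is the only measure of test performance the plan defines, since double-negative patients have no endoscopy, and the data are meant to inform the design of larger studies.

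**Working it through.** **Inputs from the documents.** TFF3 accuracy, from section 1: "The test was associated with 79.9% sensitivity and 92.4% specificity". Sample size 100 (section 3). Anticipated BE prevalence 5 to 10% (Statistical Methods).

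**Assumptions.** All marker-positive patients undergo endoscopy. The share *q* of TFF3-negative BE that has abnormal p53 is not in the documents, so it is varied from 0 to 100%.

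**Step 1: reproduce the plan's figure.** Expected TFF3-positives per 100 = true positives (TP) + false positives (FP).

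- 5% prevalence: TP = 5 × 0.799 = 3.995; FP = 95 × 0.076 = 7.22; total 11.215.
- 10% prevalence: TP = 10 × 0.799 = 7.99; FP = 90 × 0.076 = 6.84; total 14.83.

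These round to the 11% and 15% in Statistical Methods, so the inputs are the ones the plan used.

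**Step 2: nested TFF3 PPV** = TP / (TP + FP).

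- 5%: 3.995 / 11.215 = 35.6%.
- 10%: 7.99 / 14.83 = 53.9%.

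**Step 3: TFF3 PPV as written** = (TP + *q* × FN) / (TP + FP), where FN is TFF3-negative BE: 5 × 0.201 = 1.005 at 5% prevalence and 10 × 0.201 = 2.01 at 10%.

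| Assumed share *q* | 5% prevalence | Inflation (points) | 10% prevalence | Inflation (points) |
|---|---|---|---|---|
| 0 | 35.6% | 0 | 53.9% | 0 |
| 25% | 37.9% | 2.2 | 57.3% | 3.4 |
| 50% | 40.1% | 4.5 | 60.7% | 6.8 |
| 100% | 44.6% | 9.0 | 67.4% | 13.6 |

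In whole patients, one such case moves 4/11 (36%) to 5/11 (45%), or 8/15 (53%) to 9/15 (60%).

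**Step 4: chance of any inflation.** P(at least one such patient among 100) = 1 − (1 − prevalence × 0.201 × *q*)^100.

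- *q* = 25%: 22% at 5% prevalence, 40% at 10%.
- *q* = 100%: 64% at 5% prevalence, 87% at 10%.

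**Step 5: chance that the TFF3 ratio exceeds 100%.** This needs more TFF3-negative, p53-abnormal BE patients than TFF3 false positives. From the exact multinomial:

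- *q* = 25%: 0.03% at 5% prevalence, 0.15% at 10%.
- *q* = 100%: 0.45% at 5% prevalence, 3.0% at 10%.

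**Step 6: scale.** The exact (Clopper-Pearson) 95% interval for 4/11 is 10.9 to 69.2%. The expected inflation is small beside it.

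**p53.** The documents give no p53 positivity rate, p53 accuracy or dysplasia rate, so no expected value can be computed. With invented counts for illustration only: if 3 patients with abnormal p53 have endoscopy and 1 has dysplasia, the nested PPV is 1/3 (33%), and one dysplasia case positive on TFF3 only makes it 2/3 (67%). With 1 p53-abnormal patient, who has dysplasia, and 1 dysplasia case positive on TFF3 only, the formula returns 2/1 (200%). Exceeding 100% requires more TFF3-only dysplasia cases than p53-abnormal patients without dysplasia, which is possible only with very small counts.

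**The case against.** The best reply is that this is shorthand. Each quantity is labelled the PPV of a named test, and a PPV is by definition the diseased share of test-positives. Secondary Objectives puts that nesting into words, so a competent analyst would restrict the numerator without being told. That is probably what was intended. It does not settle the matter, because Secondary Objectives names no marker. Under the Completion text in section 6, a positive Cytosponge test has to include patients positive on p53 alone, since they too go on to endoscopy. On that usage Secondary Objectives describes an either-marker PPV, which differs from the TFF3 formula. Nothing in the text repairs the p53 formula for dysplasia.

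The second reply concerns size. The upper figures need every TFF3-negative BE case to have abnormal p53, and nothing in the documents supports that; section 2 presents p53 expression as a predictor of later dysplasia or cancer, not as a marker of BE. Full uptake of endoscopy is also assumed. Incomplete uptake would lower the chance that an inflating patient is seen, though uptake that does not depend on marker or disease status leaves the expected values in the table unchanged. These limits stand. So does the remark that the PPVs are descriptive secondary outcomes in a pilot of 100, with no test, stopping rule or sample size resting on them. They bear on how serious the error is, not on whether the formulas are correct.

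**Conclusion.** The concern holds. Applied exactly as written, both formulas give a wrong, upward-biased ratio whenever a diseased patient positive only on the other marker undergoes endoscopy; without such a patient they give the correct PPV. For TFF3, with full uptake, the expected inflation runs from 0 to 9.0 points at 5% prevalence and from 0 to 13.6 points at 10%, across the whole range of the unknown share. At a 25% share it is 2.2 and 3.4 points. A TFF3 value above 100% is very unlikely, at most about 3%. For p53 the direction is certain but the size is not known. This should be fixed: the rule is wrong as stated and the correction is nearly free, but the expected effect on TFF3 is modest next to the sampling error.

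**What to change.** Restrict each numerator to the patients in its own denominator:

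- **TFF3 PPV** = TFF3-positive patients with endoscopic and histologic BE at follow-up endoscopy / TFF3-positive patients who had follow-up endoscopy.
- **p53 PPV** = p53-abnormal patients with BE-associated dysplasia at follow-up endoscopy / p53-abnormal patients who had follow-up endoscopy.

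Reword the PPV sentence in Secondary Objectives so that it names the marker and covers both definitions.

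Two optional additions: report on a separate line any disease found in patients positive only on the other marker, and state whether adenocarcinoma found at endoscopy counts in the p53 numerator.

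The cost is two reworded numerators and one aligned sentence. No extra data or visits are needed, and the sample size does not change.
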